3. CHARACTERISTICS OF THE RESEARCH POPULATION

3.1. Subject Characteristics

Number of Subjects:

It is estimated that approximately 200 patients will be included for this study. The individual number for each group will vary based on screening.

Gender and Age of Subjects:

No restrictions apply to gender of the study subjects. Only adult, non-pregnant patients will be included, defined as 18 years of age or older.

a) Racial and Ethnic Origin:

No restrictions apply to race or ethnic origin of the study subjects.

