13. DATA ANALYSIS AND MONITORING

13.1. Sample Size Determination

There are limited data for proper evaluation of a sample size. However, there was a smaller presented study that had a dramatic decrease in norepinephrine dose in patients on a β -blockers or ACE-inhibitors prior to admission for patients in circulatory shock of any kind.⁷ Using these data, estimated 48h cumulative mean dose for norepinephrine patients not on anti-hypertensives will be 50 mg (SD = 10) and estimated 48h cumulative mean dose for norepinephrine for beta blocker, ACE-Inhibitor, and beta-blocker + ACE-Inhibitor groups will be 25 mg (SD = 10). Using a 4-way fixed effects ANOVA power calculation with estimated effect size from previous study ($f = 1.08$) the total sample size would be 16

F tests – ANOVA: Fixed effects, omnibus, one-way

Analysis: A priori: Compute required sample size

Input: Effect size f	= 1.0825318
α err prob	= 0.05
Power (1- β err prob)	= 0.95
Number of groups	= 4
Output: Noncentrality parameter λ	= 23.4375020
Critical F	= 3.2388715
Numerator df	= 3
Denominator df	= 16
Total sample size	= 20
Actual power	= 0.9609969

However, the current proposed study is specifically looking at septic shock and the anticipated effect is unknown. Therefore, using a 4-way fixed effects ANOVA power calculation with a medium effect ($f = 0.25$) has a total sample size of 180 patients.

F tests – ANOVA: Fixed effects, omnibus, one-way

Analysis: A priori: Compute required sample size

Input: Effect size f	= 0.25
α err prob	= 0.05
Power (1- β err prob)	= 0.80
Number of groups	= 4
Output: Noncentrality parameter λ	= 11.2500000
Critical F	= 2.6559389
Numerator df	= 3

Denominator df	= 176
Total sample size	= 180
Actual power	= 0.8039869

A list of ICU patients will be generated by the corresponding ICD-9 and ICD-10 codes for septic shock during the inclusion time frame, randomized and screened until reaching the minimum power and equal groups (n = 200, 50 patients in each group)

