13.2. Planned Statistical Analysis

All data will be reported using descriptive statistics with mean (SD) used to describe normally distributed data and median (interquartile range [IQR]) used for non-normal data or data with a significant number of outliers. Distribution of data and assessment of normality will be analyzed. Chi-squared, Fisher's Exact and Student's t-test as appropriate will be used to assess differences among the study cohorts. A 4-way fixed effects ANOVA will be utilized for the primary outcome, cumulative vasopressor dose at 48 hours. *Post hoc* pairwise comparisons will be completed between groups using Bonferroni's, Turkey, or Hochberg's GT2 depending on final group size and variance. Statistical support for data evaluation will be sought out if necessary.

REFERENCES

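### Section 13.2 lets variance decide the post hoc test, but all three listed tests pool the variance, so none of them handles unequal variances

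*Combined protocol and SAP*

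**What the plan says.** Section 13.2 sets the primary analysis: "A 4-way fixed effects ANOVA will be utilized for the primary outcome, cumulative vasopressor dose at 48 hours". Despite the label, the software output in Section 13.1 shows a one-way design with four groups, so there are six pairwise comparisons. These are to use "Bonferroni's, Turkey, or Hochberg's GT2 depending on final group size and variance" (the second name is evidently Tukey). No pattern of sizes or variances is tied to any of the three tests.

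For other comparisons, "Chi-squared, Fisher's Exact and Student's t-test as appropriate will be used to assess differences among the study cohorts". The section names no Welch test and no separate-variance post hoc test.

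On cohort sizes the protocol points two ways. Section 13.1 aims for 50 in each cohort, 200 in all. Section 3.1 says: "The individual number for each group will vary based on screening". The only SDs given are the planning values in Section 13.1, which are 10 mg in every cohort (means 50 mg unexposed, 25 mg in each exposed cohort).

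**The concern.** Making variance a criterion for the choice suggests that one of the options suits unequal variances. In standard form none does. Bonferroni after ANOVA, Tukey and Hochberg's GT2 all divide the difference in means by a standard error built from one pooled within-group variance. The omnibus F test and Student's t-test pool as well.

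If one cohort is more variable, pooling understates the standard error for pairs that include it (unless that cohort is also much the largest) and overstates it for the rest. The first kind of pair then gives too many false positives, and the second kind loses power. A cumulative dose cannot be negative, and its mean is thought to differ up to two-fold between cohorts, so unequal spread is plausible. The documents do not establish it. If the unexposed cohort were the variable one and sizes were equal, the inflated pairs would be the unexposed-versus-exposed contrasts, which are the ones in the hypothesis.

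**Working it through.** **1. The plan's own figure.** Inputs from Section 13.1: "Number of groups = 4", "α err prob = 0.05", "Power (1- β err prob) = 0.80" and f = 0.25. With λ = f²N = 0.0625 × 180 = 11.25 and df (3, 176), critical F is 2.6559 and power 0.8040. This reproduces "medium effect ($f = 0.25$) has a total sample size of 180 patients". At N = 200 power is 0.848. The sample size is not in question here.

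**2. The three tests differ very little.** Each compares |mean_i − mean_j| / √[MSE(1/n_i + 1/n_j)] with a critical value. At N = 200 (196 df) these are Tukey 2.591, GT2 2.657 and Bonferroni 2.665. The statistic and the pooled MSE are the same throughout.

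**3. Per-pair error by hand.** The documents give no unequal SDs, so I assume one SD doubled, 20 against 10, with no true difference in means. Normal tails are used as an approximation; with equal SDs, 2.591 corresponds to 0.96% per pair.

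*50 per cohort, one SD of 20.* MSE = (400 + 100 + 100 + 100)/4 = 175. The variance assumed for every difference is 175 × 2/50 = 7.
- Pair with the high-SD cohort: true variance (400 + 100)/50 = 10. The effective cut-off is 2.591/√(10/7) = 2.168, two-sided error 3.0%.
- Any other pair: true variance (100 + 100)/50 = 4. The cut-off is 2.591/√(4/7) = 3.428, error 0.06%.

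*Sizes 100/50/30/20 (assumed), SD of 20 in the smallest cohort.* MSE = (99×100 + 49×100 + 29×100 + 19×400)/196 = 129.1. For largest against smallest, the assumed variance is 129.1 × (1/100 + 1/20) = 7.745 and the true variance 100/100 + 400/20 = 21. The cut-off is 2.591/√(21/7.745) = 1.574, error about 11.6%.

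*Same sizes, SD of 20 in the largest cohort.* MSE = (99×400 + 49×100 + 29×100 + 19×100)/196 = 251.5. The pair with the highest error is 100 against 50: assumed variance 7.546, true variance 400/100 + 100/50 = 6, cut-off 2.906, error about 0.4%.

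**4. Familywise error by simulation.** Equal means, normal data, 40,000 replicates, six pairs.

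| Sizes | SDs | Tukey | Bonferroni | GT2 | Games-Howell | Bonferroni-Welch |
|---|---|---|---|---|---|---|
| 50 each | all 10 | 4.9% | 4.0% | 4.1% | 5.0% | 4.0% |
| 50 each | 20/10/10/10 | 6.6% | 5.7% | 5.8% | 4.8% | 3.9% |
| 50 each | 30/10/10/10 | 8.0% | 7.2% | 7.3% | 4.6% | 3.6% |
| 100/50/30/20 | all 10 | 5.1% | 4.3% | 4.3% | 5.2% | 4.3% |
| 100/50/30/20 | 10/10/10/20 | 16.4% | 15.0% | 15.2% | 4.7% | 3.8% |
| 100/50/30/20 | 20/10/10/10 | 0.7% | 0.6% | 0.6% | 5.1% | 4.1% |

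Simulated per-pair error agrees with step 3: 3.3% and 0.06% in the second row, and a maximum of 12.0% and 0.4% in the last two rows. Games-Howell gives about 1.1% for each pair in the second row. Running Tukey only after a significant F leaves 14.6% in the fifth row, so the omnibus test does not protect.

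**5. Skewed data.** For the fifth-row layout with lognormal errors (assumed log-SD 0.6 and 1.0; 10,000 replicates), Games-Howell gives 7.3% and 10.6%. With equal SDs and log-SD 1.0 it gives 7.6%, against 4.7% for Tukey.

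**The case against.** The strongest reply is that Section 13.1 screens until there are 50 per cohort, and at that design one doubled SD costs only one or two points of familywise error. That stands for the overall rate. It does not stand for single pairs, where 3% and 0.1% offset each other inside an average near 6.6%.

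A reader might take 16% as the expected error rate. The documents do not support that. It needs sizes that appear nowhere in them, and the larger SD in the smallest cohort with no difference in means. If spread simply rose with the mean, equal means would bring equal SDs and an error near 5%. If the unexposed cohort were both largest and most variable, the pooled tests would be conservative (about 0.7%). The only documented SDs are equal, although they are planning values for a calculation that the protocol sets aside because the effect in septic shock is unknown.

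A reader might also infer that choosing among three tests after seeing the data leaves material room for a favourable result. It does not. The statistic is the same and Tukey has the smallest critical value, so picking the best of the three gives exactly Tukey's error rate, about one point above the others.

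Finally, Bonferroni is an adjustment and would be sound if applied to Welch tests. Section 13.2 does not exclude this, but the only t-test it names is Student's. Bonferroni on two-sample Student tests still gives 11.5% in the fifth row of the table, though only 4.0% in the second.

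**Conclusion.** The point holds as a minor one. Section 13.2 makes variance a selection criterion but offers no procedure, in standard form, that responds to it. The size of the effect depends on SDs, and possibly cohort sizes, that the documents do not give. At the planned 50 per cohort with one SD doubled, Tukey familywise error is about 6% to 7%, with per-pair error about 3% or about 0.1% where roughly 1% is intended. If cohort sizes vary as Section 3.1 allows, the illustrative 100/50/30/20 split gives about 0.6% to 16%, in either direction. These figures assume normal data and no true differences. They do not show that the trial's error rate will be inflated, only that the stated rule cannot prevent it.

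**What to change.** In Section 13.2, name Welch's ANOVA for the omnibus test and Games-Howell for the six pairwise comparisons (or Bonferroni- or Holm-adjusted Welch tests) as the single procedure, and delete the choice by final size and variance.

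Games-Howell should not be presented as safe in all conditions. Section 13.2 itself expects that some data may be non-normal, and step 5 shows about 7% to 11% on skewed raw doses with unequal sizes. Add a sensitivity analysis on log-transformed dose, noting that it compares geometric rather than arithmetic means. State how a zero total would be handled: Section 5.1 lists vasopressin but gives no norepinephrine conversion for it, so a patient on vasopressin alone could have a zero equivalent dose.

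The cost is two or three sentences and standard software. There is a slight loss of power if variances are equal, and a larger one for pairs involving a high-SD cohort. In an illustration with 50 per cohort, means 2, 1, 1 and 0.45 and SD equal to the mean, power for cohort 1 against 2 is about 71% with Games-Howell and 87% with Tukey, whose error term is too small for that pair. In the same illustration a middle cohort against the lowest gains, about 81% against 29%, but Section 13.1 assumes no difference among exposed cohorts, so that gain should not be the reason for the change.
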